***Definition of Dose-Limiting Toxicity***

A DLT is defined as any of the following AEs occurring during Cycle 1 (6-week length), regardless of Investigator attribution to CTT1403, unless the AE can be clearly attributed to an extraneous cause (e.g., disease progression):

- Grade 4 neutropenia lasting  $> 5$  consecutive days.
- Grade 3 or 4 febrile neutropenia.
- Grade 4 thrombocytopenia lasting  $\geq 7$  days, or Grade 3 or 4 thrombocytopenia with clinically significant bleeding or requirement for platelet transfusion.
- Any nonhematologic AE  $\geq$  Grade 3, with the exceptions of Grade 3 nausea, vomiting, diarrhea, electrolyte abnormality, constipation, fever, fatigue, or skin rash that resolves to Grade  $\leq 2$  within 72 hours with optimal medical management.
- Any other treatment-related toxicity that results in delay of Cycle 2 administration of CTT1403 by  $> 21$  days and/or toxicity considered by the Investigator and Sponsor's medical representatives to be dose-limiting.

**Dose-Expansion Period**

A total of up to 10 patients will be treated at the MTD, or maximum tested dose (if no MTD is identified), or at a dose below the MTD (if there is evidence suggesting a favorable risk/benefit

profile) to provide further characterization of the safety, tolerability, PK, and pharmacodynamics of CTT1403.

#### **Duration of Treatment and Study Participation**

Patients will be administered CTT1403 once every 6 weeks for up to two doses in the absence of disease progression by PWCG3 criteria, unacceptable toxicity, another discontinuation criterion is met, withdrawal of consent, or closure of the study by the Sponsor.

Following completion of treatment, patients will undergo EOT assessments 30 (+ 7) days after their last dose of study drug, and will continue to be followed via telephone for survival status and clinical evidence of disease progression.

#### **Number of Patients (planned)**

A total of up to 43 patients will be enrolled, consisting of up to 33 patients during the dose-escalation period of the study, and approximately 10 patients during the dose-expansion period of the study, if this period is warranted.

#### **Inclusion Criteria (Dose-Escalation and Dose-Expansion Periods)**

To be enrolled in the study, patients will be required to meet all of the following criteria:

1. Patients must have histologically confirmed prostate adenocarcinoma that is metastatic and castration resistant (mCRPC). Patients with de novo small cell carcinoma of the prostate are excluded from participation.
2. At least 3 metastatic foci avid for PSMA-specific PET agent (CTT1057) uptake on Screening PSMA PET. PSMA avidity is defined as  $SUV_{max} >$  mediastinal blood pool.
3. Has received docetaxel, ineligible for docetaxel, or refused docetaxel for the treatment of prostate cancer.
4. Has progression by the PCWG3 criteria during or after treatment with abiraterone, enzalutamide, and/or apalutamide.
5. Has serum testosterone  $< 50$  ng/dL during screening. Patients without a history of bilateral orchiectomy are required to remain on luteinizing hormone-releasing hormone (LHRH) analog during the course of protocol therapy.
6. Male Age  $\geq 18$  years.
7. Has Eastern Cooperative Oncology Group (ECOG) performance status of 0 or 1 (see Appendix 2).
8. Demonstrate adequate organ function as defined below:

##### Adequate bone marrow function:

Leukocytes	$\geq 3,000/\text{mcL}$
Absolute neutrophil count (ANC)	$\geq 1,500/\text{mcL}$
Hemoglobin	$> 9 \text{ g/dL}$ and no red blood cell transfusions during the 14 days before administration of first dose of study drug
Platelets	$\geq 100,000/\text{mcL}$ and no platelet transfusions during the 14 days before administration of the first dose of study drug

##### Adequate hepatic function:

Total bilirubin	$< 1.5 \times \text{ULN}$ or direct bilirubin $< \text{ULN}$ in patients with known/suspected Gilbert's syndrome
Aspartate aminotransferase	$\leq 2.5 \times$ institutional upper limit of normal (patients with hepatic metastases must have $\text{AST}/\text{ALT} < 5 \times \text{ULN}$ )
Alanine aminotransferase	$\leq 2.5 \times$ institutional upper limit of normal

Adequate renal function:

Creatinine clearance  $\geq 60$  mL/min/1.73 m^2 as estimated by CKD-EPI equation

9. Ability to understand a written informed consent document, and the willingness to sign it.
10. Must agree to, and be capable of, adhering to the study visit schedule and other protocol requirements, including follow-up for overall survival.

**Exclusion Criteria (Dose-Escalation and Dose-Expansion Periods)**

Patients who meet any of the following criteria at screening will not be enrolled in the study:

1. Has received previous treatment with radium-223 or another radiopharmaceutical within 3 months prior to first dose of CTT1403.
2. Has received prior systemic anti-cancer therapy (excluding radiopharmaceutical) within 14 days, or 5 half-lives, whichever is shorter, prior to first dose of CTT1403.
3. Has received external-beam radiation within 14 days prior to first dose of CTT1403.
4. Has received cabazitaxel for the treatment of mCRPC.
5. Has received previous treatment with a therapeutic targeting PSMA.
6. Has had a major surgical procedure 28 days before first dose of CTT1403.
7. Has persistent clinically significant toxicities (Grade  $\geq 2$ ; per National Cancer Institute Common Terminology Criteria for AEs (NCI CTCAE) version 4.03) from previous anticancer therapy (excluding alopecia which is permitted and excluding Grades 2 and 3 laboratory abnormalities if they are not associated with symptoms, are not considered clinically significant by the Investigator, and can be managed with available medical therapies).
8. Has evidence of diffuse bone marrow involvement by prostate cancer in the judgment of study investigator.
9. Clinically significant urinary obstruction or moderate/severe hydronephrosis on baseline imaging.
10. Has an additional active malignancy requiring therapy that may confound the assessment of the study endpoints.
11. Has clinically significant cardiovascular disease including, but not limited to:
  - a. Uncontrolled or any New York Heart Association Class 3 or 4 congestive heart failure
  - b. Uncontrolled angina, history of myocardial infarction, unstable angina or stroke within 6 months before study entry
  - c. Uncontrolled hypertension or clinically significant arrhythmias not controlled by medication.
12. Has a history of untreated brain metastases (central nervous system [CNS] imaging is not required before study entry unless there is a clinical suspicion of CNS involvement).
  - a. Patients with previously treated brain metastases are eligible if lesions are stable on follow up imaging performed  $\geq 4$  weeks following completion of treatment
  - b. Patients with history of leptomeningeal disease are excluded from study participation
13. Has a condition requiring systemic treatment with either corticosteroids ( $> 10$  mg daily prednisone equivalents) or other immunosuppressive medications within 14 days before CTT1403 administration. Inhaled or topical steroids and adrenal replacement doses  $\leq 10$  mg daily prednisone equivalents are permitted.
14. Has uncontrolled intercurrent illness including, but not limited to, uncontrolled infection, disseminated intravascular coagulation, or psychiatric illness/social situations that would limit compliance with study requirements.
15. Has known positive status for chronic hepatitis B or hepatitis C (screening is not required). Chronic hepatitis B or C defined as having positive viral load at the time of study entry. Patients that are HIV+ an undetectable viral load and on stable anti-retroviral regimen for  $>12$  weeks prior to study entry will not be excluded.
16. Known or suspected myelodysplastic syndrome.
17. Has any medical condition which in the opinion of the Investigator places the patient at an unacceptably high risk for toxicities.

**Investigational Product, Dosage, and Mode of Administration**

CTT1403, a Lu-targeting PSMA radiotherapy, will be administered intravenously for up to two doses spaced 6 weeks apart.

The starting dose is displayed above.

**Duration of Treatment and Study Participation**

In the absence of treatment delays due to AEs, treatment be administered every 6 weeks, for up to 2 doses or until one of the following occurs:

1. Disease progression
2. Inter-current illness that prevents further administration of treatment
3. Unacceptable AE(s)
4. Patients decides to withdraw from the study
5. Significant patient non-compliance with protocol
6. General or specific changes in the patients' condition render the patient unacceptable for further treatment in the judgment of the investigator.
7. The patient has received 2 doses of CTT1403
8. A second dose of CTT1403 will not be given if the estimated cumulative kidney exposure exceeds 23Gy as determined by SPECT dosimetry following the first dose of CTT1403.

Following completion of treatment, patients will undergo EOT assessments 42 (+ 7) days after their last dose of study drug and will continue to be followed every 4 weeks up to 12 weeks and at 6 months post-treatment. Patients not exhibiting PD at the EOT assessment will be contacted every 90 days following final CTT1403 administration to report on disease progression for up to 6 months after last dose of study drug. Patients will undergo physical examination and lab donation of blood for assessment of CBC and creatinine every 4 weeks thereafter for 12 weeks after the last dose, until patient withdrawal from study, or death, whichever occurs first. Upon observation of delayed CBC recovery or other demonstration of drug related toxicity, the long-term observation period will be extended until recovery is observed and/or toxicities are resolved. Patients removed from study for unacceptable treatment related AEs will be followed until resolution or stabilization of all treatment related AEs Grade 2 or above.

**Reference Therapy, Dosage, and Mode of Administration**

Not applicable.

**Concomitant and Prohibited Medications**Usage of Concurrent/Concomitant Medications

Comprehensive supportive care is permitted during the study, including but not limited to anti-emetic and antidiarrheal agents, appetite stimulants, stimulants (i.e., modafinil), anticachexia therapy (ie, fish-oil supplements), antidepressants, opiate and non-opiate analgesics, antibiotics, selective use of corticosteroids, and platelet/neutrophil growth factors as indicated above.

Patients who enter the study receiving ongoing RANK ligand targeting agents, bisphosphonate or denosumab therapy may continue to receive these agents during study participation. mCRPC patients who are receiving LHRH agonists as medical castration should continue receiving these agents during the study.

In the setting of thrombocytopenia or neutropenia, administration of thrombopoietic agents (i.e., romiplostim, eltrombopag) or granulocyte-stimulatory agents (i.e., filgrastim, pegfilgrastim) is permitted in accordance with institutional or American Society of Hematology (ASH) / American Society of Clinical Oncology (ASCO) guidelines. Erythropoietin analogs are also permitted. These

agents should not be employed during Cycle 1 unless severe cytopenias consistent with a DLT are identified.

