CTT  
CTT1403 Phase 1

Name of Sponsor Cancer Targeted Technologies, Inc.
Name of Investigational Products CTT1403 –  Lu-PSMA targeting therapeutic agent CTT1057 –  F-PSMA targeting diagnostic agent, or  Ga-PSMA-11
Title of Study Phase 1 Dose Escalation/Expansion Study of CTT1403 in Patients with Metastatic Castration-Resistant Prostate Cancer (mCRPC).
Study Phase Phase 1
ClinicalTrials.gov Identifier NCT03822871
Study Center(s): University of California San Francisco
Principal Investigator Confidential
Date March 2, 2021
Study Objectives Primary Objectives Dose-Escalation Period 

• Determine the safety and tolerability of CTT1403.

• Determine the dose-limiting toxicity (DLT) and maximum tolerated dose (MTD) following a single dose

 Dose-Expansion Period 

• Determine the preliminary antitumor activity of CTT1403 in patients with mCRPC as measured by objective tumor response by Response Evaluation Criteria in Solid Tumors (RECIST) 1.1 in accordance with Prostate Cancer Working Group 3 (PCWG3) criteria.

 Secondary Objectives 

• Characterize the organ dosimetry and pharmacokinetics of CTT1403

• Determine the change from baseline in patient reported pain as assessed by Brief Pain Inventory (BPI)

Study Endpoints Primary Endpoints Dose-Escalation Period 

• Frequency of DLTs at escalating dose levels of CTT1403 during Cycle 1 (6-week period)

 Dose-Expansion Period 

• Objective response rate by RECIST 1.1

• Adverse event profile by CTCAE v5 criteria

 Secondary Endpoints 

• Assessment of PK (distribution and elimination t1/2)

• Assessment of organ dosimetry of CTT1403 by SPECT/CT imaging at various timepoints

• Change from baseline in patient reported pain as measured by Brief Pain Inventory (BPI)

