**Statistical Methods**

Randomization: No randomization will be utilized in this study.

Safety

Demographics (e.g., gender, age, race) and baseline characteristics (e.g., ECOG performance status, height, weight, and previous prostate cancer therapy) will be summarized with descriptive statistics. Treatment-emergent AEs (TEAEs) through 30 days after last dose of study drug will be summarized by MedDRA version 20.0 system organ class and preferred term. The incidences and percentages of patients experiencing each AE preferred term will be summarized with descriptive statistics. Adverse events will also be summarized by NCI-CTCAE version 4.03 grade and by causality (attribution to study treatment). Dose-limiting toxicities, Grades 3 and 4 AEs, SAEs, and AEs resulting in dose modification or treatment discontinuation will be summarized by preferred terms.

Incidences of laboratory abnormalities will be summarized with descriptive statistics. Vital signs and physical examination results will be summarized with descriptive statistics.

Efficacy

Efficacy parameters will be defined for all patients and for the Dose Expansion cohort.

The primary efficacy endpoint for Dose Expansion is the composite response rate. Composite response rate is defined as the proportion of patients achieving an objective radiographic response by RECIST 1.1 criteria and/or PSA decline > 50% from baseline.

Duration of radiographic response (DoR) is defined as the time from the date measurement criteria are first met for partial response (PR) or complete response (CR) to the date measurement criteria are first met for PD. Radiographic PFS is defined as the time from the date of initiation of treatment to the date measurement criteria are first met for radiographic PD or death from any cause, whichever occurs first (per PCWG3 criteria). PFS6 is defined as the percentage of patients alive and progression-free at 6 months (26 weeks) after the first dose of CTT1403. Distributions for PFS, DoR, duration of complete response (DoCR), and OS will be estimated by Kaplan-Meier methodology.

The mean percent change from baseline on BPI will be descriptively reported for the study cohort.

Pharmacokinetics

PK parameters values that will be calculated to assess distribution and elimination half-life and reported as a mean +/- standard deviation.

Dosimetry

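### The BPI pain summary takes no account of new or increased analgesic or steroid use, so in this single-arm study it cannot separate a CTT1403 effect from palliation

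*Combined protocol and SAP*

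**What the plan says.** All references are to the combined protocol and SAP.

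- **Permitted drugs.** Under Concomitant and Prohibited Medications, supportive care includes "opiate and non-opiate analgesics, antibiotics, selective use of corticosteroids, and platelet/neutrophil growth factors as indicated above". No stable-dose requirement is given for analgesics. Corticosteroid use is described as selective, but no on-study dose, duration or indication is stated.
- **The only steroid limit.** Exclusion 13 keeps out patients who need more than 10 mg daily prednisone equivalents "or other immunosuppressive medications within 14 days before CTT1403 administration". It is an entry rule: "Patients who meet any of the following criteria at screening will not be enrolled in the study".
- **Prohibited treatments.** Prohibited Medications/Therapies bars other anticancer agents and palliative radiation. It does not mention analgesics or corticosteroids.
- **The endpoint.** Study Endpoints lists BPI change from baseline as a secondary endpoint. It is the only patient-reported endpoint listed.
- **The analysis.** Statistical Methods (Efficacy) gives it one sentence: "The mean percent change from baseline on BPI will be descriptively reported for the study cohort". Analgesic and steroid use are not mentioned.
- **Design.** There is no randomisation and no reference therapy.

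**The concern.** Patients whose pain worsens are the ones most likely to be given more analgesia. With palliative radiation barred, drug treatment is the main palliation left. The BPI score then records the combined result of disease, CTT1403 and supportive drugs, and the planned mean uses it as it stands.

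Two distortions follow. A patient whose score falls below baseline because of an opioid counts as improved. A patient whose pain worsened and was brought back to baseline counts as unchanged. A control arm would have shown how much change occurs under supportive care alone, but there is none here. At stake is whether the study's one patient-reported result can be interpreted.

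**Working it through.** **No figure to reproduce.** The documents give no BPI standard deviation, no target change and no expected analgesic use. The structural point comes from reading the sections together, and the size is an illustration under stated assumptions.

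**Step 1: is there an on-study rule anywhere?** The concomitant-medication text permits both drug classes, the prohibited list names neither, and exclusion 13 applies at entry. The BPI analysis sentence contains no stable-analgesic baseline, no analgesic score, no handling of new or increased use and no sensitivity analysis. None of these sections closes the gap.

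**Step 2: size on the plan's own scale (percent change).** Let *m* be the mean percent change without added analgesia, *s* the share of patients who start or increase it, and *d* the percentage-point change it alone makes to their percent change from baseline. Then

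observed mean = (1 - s) × m + s × (m + d) = m + s × d,

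so the shift is s × d. Both inputs are assumptions: *s* from 10% to 50%, *d* from -20 to -50.

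| s | d = -20 | d = -30 | d = -50 |
|---|---|---|---|
| 10% | -2 | -3 | -5 |
| 20% | -4 | -6 | -10 |
| 30% | -6 | -9 | -15 |
| 50% | -10 | -15 | -25 |

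The range is 0.10 × -20 = -2 to 0.50 × -50 = -25 percentage points, in the direction of apparent improvement.

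**Step 3: what this looks like in single patients.** A patient whose score falls from 6 to 3 after starting an opioid contributes (3 - 6)/6 = -50%. A patient with baseline score B whose pain rises by w and is brought back to B by analgesia contributes 0%, where without the analgesia the entry would have been +100 × w/B. The first case creates improvement and the second conceals worsening. The planned mean shows neither.

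**The case against.** The strongest reply is that BPI is a secondary endpoint in a Phase 1 dose-escalation study, reported descriptively with no test and no threshold, and that any single-arm summary has this limitation. That is fair as to weight. It does not remove the gap, because a descriptive mean is still read as a description of what happened to pain, and a modest addition would make it readable.

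It can also be said that analgesia which only returns a worsened patient to baseline does not create improvement. That is correct. Such a patient pulls the mean toward no change, so the result is concealment rather than false benefit. Finally, the size in the table is entirely assumed. That is also correct, and the table should be read as a range of possibilities, not an estimate.

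A reader might infer three stronger claims. The documents do not support them.

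- **That the plan credits pain relief to CTT1403.** No such attribution is stated. The accurate statement is that the effects cannot be separated.
- **That corticosteroids are freely permitted.** The text says their use is selective. The term is undefined, but it is not unrestricted use.
- **That steroids inflate the response rate.** Statistical Methods counts "objective radiographic response by RECIST 1.1 criteria and/or PSA decline > 50% from baseline", so a PSA decline alone is enough for a composite response. In 10 expansion patients, one such response is 1/10 = 10 percentage points. But nothing in the documents says that corticosteroids lower PSA, so this rests on outside knowledge. The documents also disagree on the primary endpoint. Statistical Methods says "The primary efficacy endpoint for Dose Expansion is the composite response rate", while Study Endpoints lists "Objective response rate by RECIST 1.1", which has no PSA component. Disqualifying PSA responses after a steroid start could also discard genuine responses, so it is not a clear improvement.

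**Conclusion.** The point holds for BPI. Analgesics are unrestricted on study, corticosteroids have no stated on-study cap, and the planned mean percent change ignores both. Without a comparator, a change due to added analgesia cannot be separated from a CTT1403 effect, and palliated worsening can be hidden.

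The size is unknown from the documents. Under the assumptions in the table the shift is -2 to -25 percentage points.

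This is a cheap improvement to a descriptive secondary endpoint. It does not bear on the DLT assessment or the MTD, and it does not show that the response rate is biased. The schedule of events is not shown, so whether concomitant medication is recorded, and when BPI is completed, cannot be judged. The gap is in the stated analysis.

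**What to change.** Leave permitted care as it is and amend Statistical Methods (Efficacy).

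1. Keep the planned mean percent change in BPI.
2. Record analgesic and systemic steroid use, with dates and doses, at each BPI visit. Define in advance what counts as an increase over baseline use.
3. Add a prespecified analgesic-accounted result: from the date of a new or increased analgesic or systemic steroid, a patient's BPI value counts as no better than baseline. In formula, adjusted percent change = max(observed percent change, 0). Values worse than baseline stay as observed.
4. Tabulate these patients separately beside the unadjusted result. This is needed because step 3 removes apparent improvement but cannot restore worsening that analgesia brought back to baseline.

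No BPI responder category is needed, since the plan defines none.

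For PSA, make no change to who counts as a responder. At most, show RECIST and PSA responses separately and flag PSA declines first reached after an on-study steroid start.

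**Cost.** SAP wording and a little more data handling; more if concomitant medication is not already collected at BPI visits. The adjusted pain result may look less favourable, and it will also set aside any true CTT1403 benefit in patients whose analgesia increased. That is why both results should be shown.

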#### Dietary Restrictions

There are no dietary restrictions associated with this protocol.

#### Prohibited Medications/Therapies

Enrolled patients may not receive investigational or approved anticancer agents including cytotoxic chemotherapy agents, anticancer tyrosine kinase inhibitors, or therapeutic monoclonal antibodies not included as a study drug on this protocol for the duration of participation. Palliative radiation is not permitted during study enrollment.

